7.1 RECIST Criteria for response

The Response Evaluation Criteria in Solid Tumors (RECIST 1.1) guidelines³⁰ will be employed in this study. For the purposes of this study, measurable disease is defined as the presence of at least one measurable lesion. Measurable lesions must be accurately measured in at least one dimension (longest diameter in the plane of measurement is to be recorded) with a minimum size of:

- 10 mm by CT scan (CT scan slice thickness no greater than 5 mm; when CT scans have slice thickness >5 mm, the minimum size should be twice the slice thickness).
- 10 mm caliper measurement by clinical exam (lesions which cannot be accurately measured with calipers should be recorded as non-measurable).
- 20 mm by chest X-ray.

To be considered pathologically enlarged and measurable, a lymph node must be =15 mm in short axis when assessed by CT scan (CT scan slice thickness is recommended to be no greater than 5 mm). At baseline and in follow-up, only the short axis will be measured and followed.

Lytic bone lesions or mixed lytic-blastic lesions with identifiable soft tissue components that can be evaluated by cross-sectional imaging techniques such as CT or MRI can be considered measurable if the soft tissue component meets the definition of measurability described above.

‘Cystic lesions’ thought to represent cystic metastases can be considered measurable if they meet the definition of measurability described above. However, if non-cystic lesions are present in the same patient, these are preferred for selection as target lesions.

Non-measurable lesions: all other lesions, including small lesions (longest diameter <10 mm or pathological lymph nodes with 10 to <15 mm short axis), as well as truly non-measurable lesions. Lesions considered truly non-measurable include: leptomeningeal disease, ascites, pleural or pericardial effusion, inflammatory breast disease, lymphangitic involvement of skin or lung, abdominal masses/abdominal organomegaly identified by physical exam that is not measurable by reproducible imaging techniques. Blastic bone lesions are non-measurable. Lesions with prior local treatment, such as those situated in a previously irradiated area or in an area subjected to other loco-regional therapy, are not considered measurable unless there has been demonstrated progression (by RECIST 1.1) in the lesion.

Target lesions: all measurable lesions up to a maximum of two lesions per organ and five lesions in total, representative of all involved organs, should be identified as target lesions and will be recorded and measured at baseline. Target lesions should be selected on the basis of their size (lesions with the longest diameter) and their suitability for accurate repetitive measurements (either by imaging techniques or clinically). A sum of the diameters (longest for non-nodal lesions, short axis for nodal lesions) for all target lesions will be calculated and reported as the baseline sum diameters. The baseline sum diameters will be used as reference to further characterize the objective tumor response of the measurable dimension of the disease. If lymph nodes are to be included in the sum, only the short axis will contribute.

Non-target lesions: All lesions (or sites of disease) not identified as target lesions, including pathological lymph nodes and all non-measurable lesions, should be identified as non-target lesions and be recorded at baseline. Measurements of these lesions are not required and they should be followed as ‘present’, ‘absent’ or in rare cases, ‘unequivocal progression’.

7.1.1 Evaluation of target lesions

Complete response (CR): complete disappearance of all target lesions, confirmed by repeat assessments at no less than 4 weeks after the criteria for response are first met. Any pathological lymph nodes (whether target or non-target) must have reduction in short axis to <10 mm

Partial response (PR): at least a 30% decrease in the sum of diameters of target lesions, taking as reference the baseline sum longest diameter. This must be confirmed by repeat assessment at no less than 4 weeks after the criteria for response are first met.

Progressive disease (PD): at least a 20% increase in the sum of diameters of target lesions, taking as reference the smallest sum on study (this may include the baseline sum). The sum must also demonstrate an absolute increase of at least 5 mm.

Stable Disease (SD): neither sufficient decrease to qualify for partial response nor sufficient increase to qualify for progressive disease.

7.1.2 Special notes on the assessment of target lesions

- Lymph nodes identified as target lesions should always have the actual short axis measurement recorded even if the nodes regress to below 10 mm on study. When lymph nodes are included as

target lesions, the ‘sum’ of lesions may not be zero even if complete response criteria are met since a normal lymph node is defined as having a short axis of <10 mm.

- Target lesions that become ‘too small to measure’. While on study, all lesions (nodal and non-nodal) recorded at baseline should have their actual measurements recorded at each subsequent evaluation, even when very small. However, sometimes lesions or lymph nodes become so faint on a CT scan that the radiologist may not feel comfortable assigning an exact measure and may report them as being ‘too small to measure’, in which case a default value of 5 mm should be assigned.
- Lesions that split or coalesce on treatment. When non-nodal lesions ‘fragment’, the longest diameters of the fragmented portions should be added together to calculate the target lesion sum. Similarly, as lesions coalesce, a plane between them may be maintained that would aid in obtaining maximal diameter measurements of each individual lesion. If the lesions have truly coalesced such that they are no longer separable, the vector of the longest diameter in this instance should be the maximal longest diameter for the ‘coalesced lesion’.

7.1.3 Evaluation of non-target lesions

Complete Response (CR): Disappearance of all non-target lesions and normalization of tumor marker levels. All lymph nodes must be non-pathological in size (<10 mm short axis).

Non-CR / Non-PD: Persistence of one or more non-target lesion(s) and/or maintenance of tumor marker levels above normal limits.

Progressive Disease (PD): Unequivocal progression of existing non-target lesions.

- When patient has measurable disease. To achieve ‘unequivocal progression’ on the basis of the non-target disease, there must be an overall level of substantial worsening in nontarget disease such that, even in presence of SD or PR in target disease, the overall tumor burden has increased sufficiently to merit discontinuation of therapy. A modest ‘increase’ in the size of one or more non-target lesions is usually not sufficient to qualify for unequivocal progression status.
- When patient has only non-measurable disease. There is no measurable disease assessment to factor into the interpretation of an increase in non-measurable disease burden. Because worsening in non-target disease cannot be easily quantified, a useful test that can be applied is to consider if the increase in overall disease burden based on change in non-measurable disease is comparable in magnitude to the increase that would be required to declare PD for measurable disease. Examples include an increase in a pleural effusion from ‘trace’ to ‘large’ or an increase in lymphangitic disease from localized to widespread.

7.1.4 New lesions

The appearance of new malignant lesions denotes disease progression.

- The finding of a new lesion should be unequivocal (i.e., not attributable to differences in scanning technique, change in imaging modality or findings thought to represent something other than tumor, especially when the patient’s baseline lesions show partial or complete response).

- If a new lesion is equivocal, for example because of its small size, continued therapy and follow-up evaluation will clarify if it represents truly new disease. If repeat scans confirm there is definitely a new lesion, then progression should be declared using the date of the initial scan.
- A lesion identified on a follow-up study in an anatomical location that was not scanned at baseline is considered a new lesion and disease progression.

Cytology and Histology: if the measurable disease is restricted to a solitary lesion, its neoplastic nature should ideally be confirmed by cytology or histology. These techniques can be used to differentiate between PR and CR in rare cases.

The cytological confirmation of the neoplastic origin of any effusion that appears or worsens during treatment when the measurable tumor has met criteria for response or stable disease is mandatory to differentiate between response, stable disease, and progressive disease.

7.1.5 Evaluation of response

Evaluation of Best Overall Response: the best overall response recorded from the start of the treatment until disease progression/recurrence (taking as reference for progressive disease the smallest measurements recorded since the treatment started). In general, the patient's best response assignment will depend on the achievement of both measurement and confirmation criteria.

Table 7-1-5 provides a summary of the overall response status calculation at each time point for patients who have measurable disease at baseline.

Table 7-1-5-1 Evaluation of best overall response in patients with measurable disease

Target Lesions	Non-target Lesions	New Lesions	Overall Response
CR	CR	No	CR
CR	Non-CR/Non-PD	No	PR
CR	Inevaluable	No	PR
PR	Non-PD/or not all evaluated	No	PR
SD	Non-PD/or not all evaluated	No	SD
Not all evaluated	Non-PD	No	Inevaluable
PD	Any	Yes or No	PD
Any	PD	Yes or No	PD

Any	Any	Yes	PD
-----	-----	-----	----

Note:

Patients with a global deterioration of health status requiring discontinuation of treatment without objective evidence of disease progression at that time should be reported as "symptomatic deterioration". Every effort should be made to document the objective progression even after discontinuation of treatment.

In some circumstances it may be difficult to distinguish residual disease from normal tissue. When the evaluation of complete response depends upon this determination, it is recommended that the residual lesion be investigated (fine needle aspirate/biopsy) before confirming the complete response status.

When patients have non-measurable (therefore non-target) disease only, Table 7-1-5-2 is to be used.

Table 7-1-5-2 Evaluation of best overall response in patients with measurable disease

Non-target lesions	New lesions	Overall response
CR	No	CR
Non-CR/non-PD	No	Non-CR/non-PD
Not all evaluated	No	Inevaluable
Uequivocal PD	Yes or no	PD
Any	Yes	PD

Inevaluable designation: When no imaging/measurement is done at all at a particular time point, the patient is not evaluable at that time point. If only a subset of lesion measurements are made at an assessment, usually the case is also considered not evaluable at that time point, unless a convincing argument can be made that the contribution of the individual missing lesion(s) would not change the assigned time point response. This would most likely happen in the case of PD.

7.2 Guidelines for Evaluation of Measurable Disease

The same method of assessment and the same technique should be used to characterize each identified and reported lesion at baseline and during follow-up. CT is the best currently available and reproducible method to measure lesions selected for response assessment. MRI is also acceptable in certain situations (e.g., for body scans but not for lung). Lesions on a chest X-ray may be considered measurable lesions if they are clearly defined and surrounded by aerated lung. However, CT is preferable. Ultrasound (US) should not be used to measure tumor lesions.

Clinical lesions will only be considered measurable when they are superficial and ≥ 10 mm in diameter as assessed using calipers. For the case of skin lesions, documentation by color photography, including a ruler to estimate the size of the lesion, is recommended. Tumor markers alone cannot be used to assess response. If markers are initially above the upper normal

limit, they must normalize for a patient to be considered in complete response. Cytology and histology can be used in rare cases (e.g., for evaluation of residual masses to differentiate between Partial Response and Complete Response or evaluation of new or enlarging effusions to differentiate between Progressive Disease and Response/Stable Disease). Use of endoscopy and laparoscopy is not advised. However, they can be used to confirm complete pathological response.

7.3 Confirmation Measurement/Duration of Response

Confirmation: To be assigned a status of PR or CR, changes in tumor measurements must be confirmed by repeat studies that should be performed no less than 4 weeks after the criteria for response are first met. In the case of SD, follow-up measurements must have met the SD criteria at least once after study entry at a minimum interval of 6 weeks. Progression of disease should be verified in cases where progression is equivocal. If repeat scans confirm PD, then progression should be declared using the date of the initial scan. If repeat scans do not confirm PD, then the subject is considered not to have progressive disease per RECIST 1.1.

Duration of Overall Response: The duration of overall response is measured from the time measurement criteria are met for CR/PR (whichever is first recorded) until the first date that recurrent or progressive disease is objectively documented (taking as reference for progressive disease the smallest measurements recorded since the treatment started).

The duration of overall complete response is measured from the time measurement criteria are first met for CR until the first date that recurrent disease is objectively documented.

Duration of Stable Disease: Stable disease is measured from the start of the treatment until the criteria for progression are met, taking as reference the smallest measurements recorded since the treatment started.

Progression Free Survival (PFS): PFS is defined as the time from the date of first study treatment to the date of the first documented disease progression or death due to any cause. If a patient has not progressed or died at the date of the analysis cut-off or when he/she receives any further anti-cancer therapy, PFS is censored at the time of the last tumor assessment before the cut-off or the anti-cancer therapy date.

Time to Treatment Failure: Time from administration of the initial dose of ibrutinib until study discontinuation for any reason (e.g. disease progression, toxicity, death, withdrawal of consent).

Biochemical marker response will be defined as $\geq 50\%$ reduction in tumor marker from baseline.

8. Statistical Considerations

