5.4 Interruption or Discontinuation of Treatment

Patients may be removed from study for the following reasons:

- Documented disease progression or symptomatic tumor progression. In the case of symptomatic tumor progression, all efforts should be made to document disease status radiologically prior to removal from study;
- Occurrence of unacceptable toxicity (see table 5-2 regarding dose modifications for toxicity). Patients removed from treatment for intolerable toxicity should still be followed with regular tumor assessments until disease progression or start of a new treatment;
- Patient has been off treatment for >3 weeks;
- The patient chooses to terminate participation in the study;
- At the discretion of the investigator;
- If, at any time, the constraints of this protocol are detrimental to the patient's health and/or the patient no longer wishes to continue protocol therapy, protocol therapy shall be discontinued. In this event the study chairs should be notified, the reasons for discontinuation should be documented, and the patient should be followed as appropriate per study.

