8.2 Endpoints to be followed

Efficacy Endpoints

- Tumor response rate using RECIST (Primary endpoint);
- OS, determined from the time of drug administration to death from any cause (Secondary endpoint);
- PFS, determined as the time from administration of the initial dose of ibrutinib until objective tumor progression using RECIST, or death (Secondary endpoint);
- Duration of response, defined as time from first observation of an objective response which is subsequently confirmed, to first disease progression or death due to any cause (Secondary endpoint);
- Changes in health-related quality of life, as assessed by EORTC questionnaires EORTC QLQ-C30 and QLQ GI.NET21 (see section 11).

Safety Endpoint

Safety assessments will consist of monitoring and recording all adverse events and serious adverse events, the regular monitoring of hematology and blood chemistry parameters and regular physical examinations. Adverse events will be evaluated continuously throughout the study. Safety and tolerability will be assessed according to the NIH/NCI Common Terminology Criteria for Adverse Events version 4 (CTCAE v4) available at: http://ctep.cancer.gov/protocolDevelopment/electronic_applications/ctc.htm. All adverse events will be documented on the adverse event CRF.

Exploratory Analyses (refer to Section 6.3)

As part of this study, we will explore the correlation between early biochemical response and response rates or PFS. Early biochemical responders will be defined as patients with elevated chromogranin A (CgA) who experience a major reduction (>50%) or normalization of their CgA between their baseline (pretreatment) measurement and their follow-up assessment 3 months later.

We also plan to undertake an exploratory analysis of blood- and tissue-based markers that may correlate with the clinical outcomes observed in the study. Exploratory markers will include the measurement of serum Tryptase- β 2 and the determination of the presence and activation of mast cells in the tumor tissue samples.

Archival pathology specimens will be reviewed at the study institution (Moffitt Cancer Center) for determination of mitotic rate (number of mitoses per 10 high-powered fields) and Ki-67 index.

This study is not sufficiently powered to establish definitive outcome for the correlative endpoints. These results will be considered hypothesis generating and any comparison with a significant alpha <0.05 will be deemed of sufficient interest to warrant further evaluation.

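### A patient removed for symptomatic progression without RECIST progression on scan is censored for PFS once new therapy starts, which can push the secondary PFS estimates upward

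*Combined protocol and SAP*

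**What the plan says.** All references are to the combined protocol and SAP.

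- **Leaving the study (5.4).** The first listed reason is "Documented disease progression or symptomatic tumor progression", so clinical progression is an alternative to documented progression. For such patients, "all efforts should be made to document disease status radiologically prior to removal from study".
- **Classification (7.1.5).** Patients whose global health declines enough to stop treatment "without objective evidence of disease progression at that time should be reported as" symptomatic deterioration. Neither response table scores this as progressive disease. The section adds: "Every effort should be made to document the objective progression even after discontinuation of treatment".
- **PFS event.** Section 7.3 runs PFS to "the date of the first documented disease progression or death due to any cause". Section 8.2 is narrower: "until objective tumor progression using RECIST, or death".
- **Censoring (7.3).** For a patient without an event at the cut-off or when further therapy is given, "PFS is censored at the time of the last tumor assessment before the cut-off or the anti-cancer therapy date".
- **Imaging schedule.** Scans fall every 3 cycles (12 weeks), and Table 6-5 also marks tumor imaging at the End visit. Footnote b makes an exception for patients who stop because of an adverse event or abnormal laboratory value. It does not mention symptomatic progression.
- **Analysis.** Median PFS and 1-year PFS are secondary endpoints (3.2), estimated by Kaplan-Meier (8.3). No PFS sensitivity analysis is described.

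**The concern.** Kaplan-Meier estimation assumes that a patient censored at a given time has the same outlook as those still followed. That fails here, because the patient leaves follow-up for the very reason that the tumor appears to be progressing. If no scan shows RECIST progression before new therapy starts, the plan removes the patient from the risk set without counting a failure. The remaining patients then look better than the cohort really is.

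At stake are the descriptive median and 1-year PFS in cohorts of 30 and 21. Each cohort receives a single treatment, so no concurrent arm carries the same bias. The scan instructions in 5.4 and 7.1.5 are best-effort, and neither section says how the patient counts for PFS if the scan is missing or inconclusive.

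**Working it through.** **Step 1. Which patients are affected.** Consider a patient removed for symptomatic progression or deterioration:

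| What happens next | PFS under 7.3 and 8.2 |
|---|---|
| Scan shows RECIST progression before new therapy | Event |
| Death before new therapy | Event |
| End scan done, RECIST progression not met, new therapy starts | Censored at the End scan |
| End scan missed, new therapy starts | Censored at the last earlier scan |
| No new therapy, no further scan, no death before cut-off | Censored at the last scan |

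Only the last three rows are a problem. Progression first seen after new therapy has started does not restore the event.

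**Step 2. Inputs.** The documents give no PFS assumption, so there is no stated figure to reproduce.

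- Scan interval: 84 days (Table 6-5).
- True median PFS, an assumption: 5.5, 8 and 11.4 months. The two ends are borrowed from the pNET trial described in 1.1, and 8 is a middle value.
- Share *q* of progressions that are symptomatic, lack RECIST progression and are followed by new therapy. This is not in the documents. The range shown is 5% to 30%.
- Exponential times, no deaths before progression, cut-off at 36 months.

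**Step 3. Continuous-time check.** Turning a share *q* of progressions into censorings multiplies the apparent hazard by (1 − *q*), so the apparent median is the true median × 1/(1 − *q*). The factors are 1.05, 1.11, 1.25 and 1.43 for *q* = 5%, 10%, 20% and 30%. For 1-year PFS with median *m* months:

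- true: 0.5^(12/*m*)
- apparent: 0.5^((12/*m*)(1 − *q*))

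With *m* = 8 and *q* = 20%, these are 0.5^1.5 = 35.4% and 0.5^1.2 = 43.5%, a gap of 8.1 points.

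**Step 4. Simulation with 12-week scans** (400,000 times per setting). Progression found by scan is dated at the next scan. Symptomatic cases are either censored at the last scan (plan) or counted as events on the removal date. Each cell shows 1-year PFS, plan versus counted as events. Gaps use unrounded values.

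| *q* | median 5.5 | median 8 | median 11.4 | gap (points) |
|---|---|---|---|---|
| 5% | 26.4% vs 24.7% | 40.1% vs 38.3% | 52.7% vs 51.0% | 1.7 to 1.9 |
| 10% | 28.1% vs 24.6% | 41.8% vs 38.1% | 54.3% vs 50.7% | 3.4 to 3.8 |
| 20% | 31.8% vs 24.4% | 45.6% vs 37.7% | 57.8% vs 50.4% | 7.4 to 7.9 |
| 30% | 36.1% vs 24.2% | 50.0% vs 37.5% | 61.9% vs 50.2% | 11.6 to 12.5 |

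Simulated medians land on scan dates and jump by a whole interval, so the 1-year rate is the steadier measure.

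**Step 5. Trial-sized cohorts.** At *n* = 21 and *n* = 30 (median 8 months), the mean gap was 3.8 points at *q* = 10% and 7.8 to 7.9 points at *q* = 20%. It was never negative in 3,000 simulated cohorts per setting.

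**Step 6. Does a non-progressing End scan help?** It moves the censoring date from the last scheduled scan to the exit. In this model the curve drops only at scheduled scan dates, and the patient is out of the risk set at the next one either way. A separate run (median 8 months, *q* = 20%) gave 45.7% under both censoring dates, against 37.8% when counted as events.

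**The case against.** The strongest reply is that the plan already limits the problem, and much of that stands.

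- **End scan.** Table 6-5 schedules imaging on leaving, reinforced by 5.4 and 7.1.5. A reader might infer that every patient removed for symptoms goes uncounted, or that an early exit is censored near time zero. The documents do not support this as the general case: a patient scanned at End is either an event or is censored at that scan. The End scan shrinks the affected group. It does not help a patient whose scan falls short of RECIST progression (Step 6).
- **Replacement rule.** A patient who leaves before the first follow-up scan first meets 8.4, which replaces such dropouts unless they leave for dose-limiting toxicity or progressive disease. Whether symptomatic progression counts as progressive disease there is not stated. An exit at, say, week 10 is therefore not simply a 7.3 censoring case.
- **Time to treatment failure.** Section 7.3 defines it to cover leaving the study for any cause, so it would capture these patients. It is also broader than PFS, and it is absent from the endpoint lists in 3.2 and 8.2.
- **Wording of 7.3.** Documented progression could be read to include clinical documentation. Section 8.2 and the contrast drawn in 5.4 point the other way.
- **Outside comparison.** A reader might infer that PFS will be judged against the 5.5 and 11.4 months in 1.1, with nothing to cancel the bias. The plan sets no PFS hypothesis or benchmark; its external comparison in 8.3 is response rate. The documents also do not say how the cited trial handled symptomatic progression.
- **Noise.** Near 38%, ignoring censoring, the standard error of 1-year PFS is about √(0.38 × 0.62/30) = 9 points at *n* = 30 and √(0.38 × 0.62/21) = 11 points at *n* = 21. A bias of 2 to 4 points sits well inside that. It is nevertheless systematic, and a confidence interval does not show it.

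**Conclusion.** The point holds as a cheap improvement. Under 7.3 and 8.2, a patient removed for symptomatic progression or deterioration whose End scan is missed or does not meet RECIST progression is not a PFS event, and is censored once new therapy starts. That censoring is informative and can bias median and 1-year PFS upward: about 2 points in 1-year PFS at a 5% share, 4 at 10% and 8 at 20%.

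Those sizes rest on an assumed share, exponential times, no deaths before progression, and every affected patient switching therapy before a scan shows progression. The direction does not depend on the share, provided it is above zero. An unconditional statement that PFS will be overstated goes too far, because full End imaging that confirms progression would remove the bias. The primary response-rate test and the two-stage rules are unaffected.

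**What to change.** 1. Keep RECIST PFS as the main analysis.
2. In 7.3 or 8.3, prespecify a sensitivity Kaplan-Meier analysis in which removal for symptomatic tumor progression or symptomatic deterioration counts as an event on the date of removal.
3. State in 7.3 how these patients are handled in the main analysis, and align its event wording with 8.2.
4. Report how many patients left by this route, and how many of them had an End scan.

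The cost is a few sentences and one extra curve per cohort. Section 5.2 already requires the reason for discontinuation to be recorded; the removal date should be captured with it. The downside is that the added figure will be less favourable and rests partly on investigator judgment in an open-label trial, which is why it belongs beside the RECIST analysis and not in its place.
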